## 2.0 SPECIFIC AIMS

### *Primary Aims:*

1. To compare product use patterns and biomarkers of exposure and effect based on differing instructions for oral tobacco use: a) complete substitution vs. partial substitution for cigarettes; and b) specific instructions for use vs. no instructions (*ad libitum* use).
2. To determine stabilization of product use by examining time effects for subjective (e.g., dependence), biological (e.g., biomarkers of exposure) and behavioral responses (e.g., smoking exposure and oral tobacco topography).
3. To determine important moderators of use of a product and exposure (i.e., consumer perception of the product and consumer response to the product after sampling [Project 3], nicotine metabolite ratio, nicotine dependence, gender, race and age).

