Procedures for clinic visits: Subjects will continue to complete daily diaries for tobacco and other nicotine product use. At every clinic visit, vital signs, weight, oxygen saturation and expired air CO will be obtained. At weeks 2, 4, and 8 of product use, blood, and first morning void urine collection samples will be collected. At week 6, a first morning void urine sample will be provided. Buccal cells will be collected at weeks 4 and 8. Samples from weeks 4 and 8 will be analyzed for biomarkers as described below. Samples taken at week 2 will be aliquoted and stored for future analyses governed by results from the 4 and 8 week analyses or for other future studies. Questionnaires that measure factors that may influence biomarker assessments will be administered at the time of biosample collection. All other subjective measures will be collected throughout the experimental phase. All cigarette butts, as appropriate for the study group, will be collected in a container 24 hours before the week 4 biomarker clinic visits. In addition, used and unused snus will be collected for 24 hours prior to week 4 to assess for amount of constituents that have been extracted. During this collection, time in and time out of snus products via a paper diary will be recorded to assess oral tobacco topography. At the end of experimental phase, all subjects will be strongly encouraged to quit using all tobacco products and set a quit date. A treatment manual (Clearing the Air) and treatment resources will be provided.

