## **7.0 Statistical Analysis**

This study has three primary aims: to determine the effect of instructions for use and the amount of substitution on biomarkers of exposure and patterns of oral tobacco use (primary endpoint at 4 weeks, but also assessed at 8 weeks), to determine when stabilization of product use occurs by examining the time effects for subjective, biological, topographic and behavioral responses (analysis for 2, 4, 6 and 8 weeks) and to determine important moderators for product use and exposure. Secondary aims include developing innovative measures to assess levels of exposure from smokeless tobacco and cigarettes.

Demographic and smoking history variables of those who entered the sampling phase and the trial phase will be summarized and compared to national survey data for the general population of smokers and smokers most interested in using oral tobacco products (e.g., 1). Baseline covariates will be summarized by treatment group to check that groups are balanced after randomization. Continuous measures will be summarized by mean (SD), median (range)

or other summary measures. Categorical covariates will be summarized by contingency tables. Numerical variables measured more than once at the baseline assessments will be assessed for reproducibility using the intra-class correlation coefficient and the average will be used for the baseline variable if adequate reproducibility is observed.

The primary outcome measures (tobacco use, biomarkers, subjective measures) will be assessed up to five times for each individual. The analysis of our primary aims will use linear mixed models to account for potential intra-subject correlation due to repeated measurements from a single individual. Linear mixed models are sensitive to miss-specification of the within-subject correlation structure. We will use exploratory graphical methods to identify the appropriate within-subject correlation structure. Residual plots and other diagnostic methods will be used to check other model assumptions.

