**Hypothesis 1** will be analyzed by fitting a linear mixed model for each of the outcome measures (using week 6 as the primary endpoint): total NNAL, NNN, phenanthrene tetarol, mercapturic acids, PGEM, 8-epi-PGF2α, Total nicotine equivalents; and cardiovascular risk factors.. The mean model will include an effect for time, group and a time by group interaction. Specific hypotheses will be tested by testing the significance of the appropriate contrast. A secondary analysis will be completed adjusting for important factors such as environmental toxicant exposures, nutrition, stress and health to determine the effect their inclusion has on the association between group and the outcomes. Finally, we will complete an exploratory analysis that includes a site by group interaction to determine if the group effect changes by location.

**Hypothesis 2** will be analyzed by fitting separate linear mixed models for each group using biomarkers, snus topography, cigarettes and other subjective responses as the outcome. We will test for significant time effects and present plots of the outcomes to visually represent the time effects. Stabilization will be considered to have occurred when the variance between time-points does not exceed the coefficient of variation of the measures as assessed in the usual brand smoking group.

**Hypothesis 3** will be analyzed using a linear mixed effects models with a mean model that includes time, group and potential moderators (e.g., use patterns, age, sex, dependence, subjective responses, etc.). Interactions between group and the potential moderators will be included in the model and tested to determine if the potential moderator modifies the effect of group on the outcome (total nicotine equivalents, total NNAL).

**Hypothesis 4** will be evaluated using scatter plots and other visual methods. Associations will be summarized by Pearson's or Spearman's correlation coefficient, as appropriate, and formal inference will be completed using linear regression.

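### The Hypothesis 2 stabilization rule compares a variance with a coefficient of variation, and timed topography and week-6 laboratory assays are not scheduled to support it

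*Combined protocol and SAP*

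**What the plan says.** Primary Aim 2 (section 2.0) asks when product use stabilizes. Hypothesis 2 expects a plateau by week 6.

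Section 7.0, Hypothesis 2, fits a separate mixed model in each arm to biomarkers, snus topography, cigarettes and subjective responses. It adds: "We will test for significant time effects and present plots of the outcomes to visually represent the time effects". The decision rule follows: "Stabilization will be considered to have occurred when the variance between time-points does not exceed the coefficient of variation of the measures". The reference value comes from the usual-brand arm. No unit, transformation or type of CV is given.

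On the visits used:
- The opening of section 7.0 names weeks 2, 4, 6 and 8 for the stabilization analysis of subjective, biological, topographic and behavioral responses. Primary Aim 2 likewise lists oral tobacco topography.
- Section 6.4 (Procedures for clinic visits) places the used-snus collection in the 24 hours before week 4, and states: "During this collection, time in and time out of snus products via a paper diary will be recorded to assess oral tobacco topography".
- The same paragraph states: "At weeks 2, 4, and 8 of product use, blood, and first morning void urine collection samples will be collected". Week 6 adds a urine sample only. Samples from weeks 4 and 8 are to be analyzed. Week-2 samples are stored, with later analysis depending on the week-4 and week-8 results.
- For Hypothesis 1, the opening of section 7.0 has "primary endpoint at 4 weeks, but also assessed at 8 weeks", while the Hypothesis 1 paragraph has "using week 6 as the primary endpoint".

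**The concern.** A between-time variance carries the square of the outcome's unit, and a CV carries no unit. Comparing them directly has no fixed meaning until a scale is chosen, and the plan chooses none. Nor does it say whether the CV is within-subject, between-subject or assay. Two analysts could follow the text and reach opposite verdicts from the same data.

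This matters because the rule is the only stated threshold for a primary aim. Section 3.0 explains the purpose: if use stabilizes within a few weeks, product-switching trials can be that short. The planned tests and plots describe change over time but set no limit on how much change counts as stable. A non-significant time effect does not demonstrate stability.

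The schedule raises a second problem. Some outcomes to which the rule is to be applied lack the repeated measurements or the reference CV that it needs.

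**Working it through.** The plan gives no numerical example of the rule, so there is no figure to reproduce. All means and CVs below are assumptions (CV 0.2, 0.4, 0.6). The documents give no NNAL unit and count smoking in cigarettes; packs of 20 are only an illustration.

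**1. Literal reading, untransformed data.** Multiplying an outcome by c multiplies its variance by c² and leaves the CV unchanged. The rule amounts to SD ≤ √CV in whatever unit is used.
- NNAL 1.50 then 1.20 pmol/mg: variance = 0.15² + 0.15² = 0.045, stable at all three CVs. In fmol/mg: 0.045 × 1000² = 45,000, stable at none.
- Cigarettes per day 12, 11.5, 11, 10.5 (mean 11.25): variance = (0.75² + 0.25² + 0.25² + 0.75²)/3 = 0.417, not stable at CV 0.2 or 0.4, stable at 0.6. In packs: 0.417/20² = 0.00104, stable at all three.

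**2. Unit-free readings.** Let r be the ratio of the later to the earlier visit mean, with two visits and noise-free means.
- Log variance: (ln r)²/2 ≤ CV gives r = exp(−√(2·CV)) = 0.531, 0.409, 0.334. Falls of up to 47%, 59%, 67% pass.
- CV of visit means: √2(1 − r)/(1 + r) ≤ CV gives r = 0.752, 0.559, 0.404. Falls of up to 25%, 44%, 60% pass.

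These are upper limits. If the log variance is taken within subject, visit noise uses part of the allowance. With independent log-normal error, the expected log variance is (ln r)²/2 + ln(1 + CV²), and the limits drop to about 43%, 51%, 53%.

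**3. Post-baseline data among weeks 2, 4, 6 and 8** (section 6.4 against Table 2).

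| Outcome | Weeks available |
|---|---|
| Diary counts, exhaled CO | 2, 4, 6, 8 |
| Urinary toxicants | 2, 4, 8 by Table 2; 4, 8 by section 6.4 |
| Nicotine equivalents, C-reactive protein, hematology | 4, 8 |
| Time-in/time-out topography | 4 |

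One time point has no between-time variance. Table 2 marks no laboratory assay row at week 6; that week's urine appears only among the biobank samples, and no blood is drawn.

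**4. Reference CV.** The usual-brand arm is given no snus in weeks 1-8 (section 6.4), so it supplies no concurrent CV for any snus outcome. Its snus data from the sampling week and after week 8 are not a usual-brand reference.

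**5. Check of a replacement.** Illustrative margin 0.80-1.25 for the ratio of geometric means, 100 subjects retained per arm, independent log-normal visit errors. Log SD σ = √ln(1 + CV²) = 0.198, 0.385, 0.555, and SE = σ√(2/100) = 0.0280, 0.0545, 0.0785.
- No true change, weeks 4 versus 8: the 95% intervals, centered on a ratio of 1, are 0.946-1.057, 0.898-1.114, 0.856-1.168. Stability is shown in >99%, 97%, 61% of trials.
- Steady 10% fall per visit (1 − 0.9³ = 27% over weeks 2 to 8): the 6-versus-8 comparison passes with probability Φ[(ln(0.9/0.8) − 1.98·SE)/SE], which gives about 99%, 57%, 32%, matching simulation. The 4-versus-8 ratio is 0.81, almost on the margin, so the declaration nearly always falls at week 6 and rests on one comparison.

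**The case against.** The strongest reply is that a working statistician would read the rule as variation against variation, so the unit cancels, and that smoking is counted in cigarettes throughout. This stands in part: the unit reversal belongs to the literal reading on untransformed data, and the pack example is only an illustration. But the text selects neither unit-free reading. The two give different limits, both let large falls in visit means pass, and the type of CV is still open.

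A second reply is that snus topography may include diary pouch counts. Those are repeated, and the single-time-point problem does not touch them. A reader might infer that no snus-use outcome can be followed over time; the documents do not support that. Nor does Table 2 say anything about timing: its week-4 row marks collected samples. The evidence for a single timed recording is the text of section 6.4.

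A third reply is that biological responses include CO, which is measured at all four weeks; that making week-2 assays depend on later results is a reasonable staged approach; and that the biobank text allows further assays. All true. Similar laboratory values at weeks 4 and 8 would also support a plateau by week 6. The gap matters if those values differ, because the scheduled assays could not then show a plateau by week 6.

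Finally, the mixed models, time-effect tests and plots remain usable. A reader might infer that Hypothesis 2 cannot be analyzed at all, which goes too far. What is missing is a usable definition of stable.

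**Conclusion.** The concern holds in this form. The stated threshold for Primary Aim 2 is dimensionally inconsistent. Read literally, its verdict can be reversed by the reporting unit. Read charitably, it tolerates falls of up to 47/59/67% (log variance) or 25/44/60% (relative variation) between two visits. Those figures assume CVs of 0.2/0.4/0.6 and noise-free means, and within-subject noise lowers them. Dimensional inconsistency needs no assumption.

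The rule cannot be applied to time-in/time-out topography, has no concurrent reference CV for snus outcomes, and is to be used at a week for which no laboratory assay is scheduled.

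A reader might infer that the randomized comparisons under Hypothesis 1 or the sample size are undermined by the rule. The documents do not support that: neither the Hypothesis 1 model nor the NNAL calculation uses it. The week-4 versus week-6 conflict over the Hypothesis 1 endpoint is a separate inconsistency, on which the assay schedule also bears. The rule should be corrected before the stabilization analysis is run.

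**What to change.** - **Criterion.** In each arm, compare each visit with every later visit by the ratio of geometric means and its 95% confidence interval. Call the outcome stable from the first visit at which all these intervals lie within a pre-specified margin. The last visit cannot be declared. Use same-unit differences for outcomes with zeros, and a separate pre-specified margin for snus-use outcomes.
- **Margin.** The usual-brand within-subject CV may inform it, but the sponsor should justify it and state the largest mean change it accepts per interval and cumulatively. The 0.80-1.25 used above is an illustration, not a recommendation.
- **Slow drift.** Do not date a plateau to the next-to-last visit on one comparison alone. Report the estimated trend and its interval beside it, or choose a narrower margin.
- **Topography.** Remove time-in/time-out topography from the time-effect and stabilization analyses in Primary Aim 2 and both places in section 7.0. Keep the diary counts.
- **Weeks.** Reconcile section 6.4, section 7.0 and Table 2 on assay weeks, and the two statements of the Hypothesis 1 endpoint week. Limit the laboratory plateau claim to the weeks actually assayed.

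The cost is mainly wording and some extra analysis, with no new visits or samples. Running week-2 or week-6 samples adds assay cost, and the week-6 urine cannot supply C-reactive protein or hematology. The laboratory claim becomes narrower, and stability will often remain unproven for noisy outcomes, as the 61% above at CV 0.6 shows.

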Smoking Usual Brand Condition. Subjects in this condition will undergo all the procedures as those subjects assigned to Camel Snus, except they will be told to smoke their usual brand of cigarettes and follow their normal patterns. At the end of the 8-week period, they will be offered the product for up to 8 weeks, with a choice of how they want to use the product. They will return to the clinic at 9, 10 and 12 weeks for assessment of use patterns (1, 2 and 4 weeks on the product). During this period, subjects will keep daily diaries via Interactive Voice Response (IVR). After 4 weeks of product use, they will come to the clinic whenever they want products for up to 8 weeks. At these clinic visits, their tobacco use patterns will be assessed via the Daily Use Summary and subjective forms. At the end of the 8 weeks (Week 16) of snus use, subjects will bring in a first morning void urine sample for analysis of tobacco exposure measures. Subjects will be paid \$50 for the Week 16 visit. Follow-up will occur as described below after the 8-week product access period (Weeks 20, 28 and 40). If subjects in the Usual Brand Condition do not choose to use the Camel Snus, they will follow the Follow-up schedule for the snus arms.

Follow-up. Follow-up clinic visit will occur for all subjects at week 20 (12 weeks after the end of the trial period). Tobacco use status (amount and type of tobacco product use) will be determined. CO will be obtained and a first morning urine and blood sample. These samples will be stored for cotinine assessment. Follow-up calls will occur at week 12 and 32 (4 and 24-weeks post-study) and tobacco use will be assessed. Those continuing to smoke or use Camel Snus will be strongly advised to quit and treatment resources will be provided.

Product Compliance Sessions. At each visit, subjects will be asked and counseled about their use of Camel Snus. The procedures for inquiry and counseling will be standardized. An intervention manual for each of the conditions will be developed.

- Complete Substitution Condition: Subjects will be asked about any concerns or obstacles associated with only using Camel Snus. If difficulties are encountered, then subjects will be asked about why they think they are experiencing difficulties (e.g., taste,

lack of satisfaction, withdrawal symptoms) and will be asked to problem solve how to deal with these difficulties so that they can meet the requirements of the protocol.

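### The stabilization criterion has no reference value for snus use, because it is taken from the one arm that has no study snus in weeks 1 to 8

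*Combined protocol and SAP*

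**What the plan says.** Aim 2, a primary aim in section 2.0, is "To determine stabilization of product use by examining time effects for subjective (e.g., dependence), biological (e.g., biomarkers of exposure) and behavioral responses"; smoking exposure and oral tobacco topography are its examples of behavioral responses. Section 7.0 sets the times: "topographic and behavioral responses (analysis for 2, 4, 6 and 8 weeks".

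Under Hypothesis 2 the analysis is done by "fitting separate linear mixed models for each group using biomarkers, snus topography, cigarettes and other subjective responses as the outcome". Time effects are tested and plotted. One rule then defines stabilization for all of these outcomes: the variance between time-points "does not exceed the coefficient of variation of the measures as assessed in the usual brand smoking group". No other reference is named.

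Section 6.4 describes the usual-brand arm. Its subjects follow the same procedures as the snus arms, "except they will be told to smoke their usual brand of cigarettes and follow their normal patterns". Snus comes later, with the pattern of use left to the subject: "At the end of the 8-week period, they will be offered the product for up to 8 weeks, with a choice of how they want".

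**The concern.** A rule that judges stability against a reference arm needs that arm to show the measure being judged. For cigarettes, CO and biomarkers it does. For snus use it does not, because all four analysis times come before that arm has trial-phase snus.

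Section 3.0 explains the stake: if use settles within a few weeks, future product trials can be that short. Section 2.0 predicts a plateau by at least 6 weeks. If the criterion gives no threshold for pouches per day, the analyst must choose a substitute after seeing the data, and that choice can decide whether and when use is called stable.

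**Working it through.** The plan states no numerical threshold, so there is no figure to reproduce. The check is whether the rule yields a usable threshold for pouches per day.

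**Inputs**
- Rule, outcomes and analysis weeks: section 7.0.
- Usual-brand instruction and timing of the snus offer: section 6.4, Experimental period and Smoking Usual Brand Condition.
- Smokeless tobacco use in the last 3 months is an exclusion: section 6.2, Eligibility Criteria. Subjects resume smoking for a 2-week baseline after the sampling week: section 6.4, Clinical Trial Phase.
- Arm size 138: section 7.0, Sample-size determination. It is used only for illustration.

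**Formula.** CV = SD / mean.

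**Reading 1: controls follow the instruction.** Pouches per day are 0 for everyone, so mean = 0, SD = 0 and CV = 0/0, which is undefined.

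**Reading 2: a few controls stray.** Assume k of 138 use 1 pouch a day and the rest use none. Then mean = k/138, SD = sqrt[k(138 − k)/(138 × 137)], and CV = sqrt[138(138 − k)/(137k)].

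| k | CV |
|---|---|
| 1 | 11.75 |
| 3 | 6.73 |
| 7 | 4.34 |
| 14 | 2.99 |

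These values measure contamination of the control arm. They say nothing about the normal variability of snus use.

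**Reading 3: the reference is taken as 0.** Weekly means of 7.9, 8, 8.1 and 8 have variance (0.01 + 0.01)/3 = 0.0067, which exceeds 0, so almost perfectly flat use fails.

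**How far the readings differ.** Weekly means of 6, 8, 10 and 8 have variance (4 + 4)/3 = 2.67. Against the k = 14 reference of 2.99 they pass as stable. So one reading rejects a swing of 0.1 pouch and another accepts a swing of 2 pouches.

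**Units.** The rule also compares a variance (squared units) with a unitless CV. That is a separate defect. Correcting it leaves Readings 1 to 3 without a meaningful reference, since an all-zero arm has no CV on any scale.

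**Topography.** Section 6.4, Procedures for clinic visits, has used pouches collected and times in and out recorded for the 24 hours before week 4. Table 2 shows snus samples at week 4 only; its baseline entry is marked as cigarette butts only. One time-point gives no variance between time-points, so no rule can assess stabilization of this measure.

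**Other snus data in the usual-brand arm.** There are two periods: the sampling week before randomization, and the weeks after week 8 for those who accept the offer. The rule cites neither. Both are periods of first uptake, and the second is optional with a self-chosen pattern of use.

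**The case against.** The best case for the plan has four parts.

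*Time effects are still analyzed.* Hypothesis 2 plans a separate mixed model in each group, with tests and plots of time effects. Neither step needs a control reference. This stands. A reader might infer that nothing can be learned about the course of snus use, and the documents do not support that; what is missing is the formal stabilization verdict. A non-significant time effect does not replace it, because it does not demonstrate a plateau.

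*Most of Aim 2 is untouched.* This also stands. Aim 2 covers subjective, biological and behavioral responses, and the usual-brand arm supplies a reference for biomarkers, CO, cigarettes and general dependence or withdrawal measures. It would be wrong to infer that Aim 2 as a whole fails. Pouches per day is not named in the Hypothesis 2 outcome list either; it enters through the aim's wording on product use and through tobacco use as a primary outcome measure in section 7.0.

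*Controls may give product ratings.* A reader might assume they rate nothing. Section 6.4 gives controls the same procedures as the snus arms apart from the smoking instruction, and Table 1 schedules the Product Evaluation and Drug Effects/Liking scales without an exemption by arm. What controls rate is unclear, so an absent reference is not shown.

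*A cigarette CV could be borrowed.* A CV has no units, and variation in a settled habit is an arguable benchmark for a new one. But the plan does not say this, and the rule refers to the CV of the measures themselves. Nor can one conclude that a borrowed value would always or never declare stability. Assuming Poisson counts, one person's 7-day total varies by 1/sqrt(28) = 0.19 at 4 pouches a day and 1/sqrt(56) = 0.13 at 8. For a mean over 138 people the same noise is 0.189/sqrt(138) = 1.6% and 0.134/sqrt(138) = 1.1%. The outcome depends on which level is meant, and Poisson variation is doubtful in the two arms given a fixed daily number.

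**Conclusion.** The concern holds for snus-specific use measures. For pouches per day the threshold is undefined if controls follow their instruction, and not meaningful if a few do not, so the stabilization criterion cannot be applied in any of the four snus arms. Topography lacks a reference too and, with a single collection, cannot be assessed under any rule. For product ratings the plan needs clarification.

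The conclusion rests on the assumption that the usual-brand arm uses essentially no snus in weeks 1 to 8, as instructed. The stray-user figures and the Poisson figures are illustrations under stated assumptions. The conclusion depends on neither.

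This should be corrected before analysis. It affects one class of measures within a primary aim. It does not affect the randomized comparisons under Hypothesis 1.

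**What to change.** In section 7.0, Hypothesis 2:

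1. Keep the usual-brand reference only for measures that arm has: biomarkers, CO, cigarettes, and general dependence or withdrawal measures. Put both sides of that comparison on the same scale.
2. For pouches per day, define stability from the snus arms' own daily diary data. For example: use is stable from the first visit after which the 90% CI for the model-based ratio of mean use between each visit and the next stays inside a margin fixed in advance, such as 0.80 to 1.25. A ratio of group means allows for subjects with zero-use weeks, which a within-person ratio does not.
3. Report within-person variation from the diary as the noise level. Also report the ratio from the first stable visit to week 8, since small steps in one direction can each pass and still add up.
4. State that the last visit serves only as a comparator and is not itself shown to be stable.
5. Drop topography from the stabilization analysis and describe it at week 4.
6. State what controls rate on the product scales, and choose the reference for ratings accordingly.

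The cost is SAP wording; the diary data are already collected daily. The downside is that a margin must be chosen and justified in advance. The documents give no figure for it, so 0.80 to 1.25 is only an example.

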### **Hypotheses**

#### *Primary Aims:*

1. Instructions for use will lead to significant differences in patterns of use, which will be related to biomarkers of exposure.
2. Time in study will have an effect on outcome measures and will reach a plateau by at least 6 weeks.
3. Moderators for exposure will include pattern and intensity of tobacco product use. Pattern and intensity of product use will be affected by subjective responses to products,

perception of safety of the product, gender, race, age, degree of dependence and nicotine metabolism phenotype.

*Secondary Aim:*

4. Biomarkers of exposure will be related to levels of chemical constituents extracted from used oral tobacco pouch products in the complete substitution condition, plus levels of solanesol in filters in the partial substitution condition.

The outcome of this study will provide guidance on methods and measures that should be used in clinical trial assessments of tobacco products (e.g, MRTPs or new tobacco products). Furthermore, this study will novelly consider the interactions and effects of instructions of product use, perception and response to the product, and individual differences on product uptake and use and toxicant exposure.

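### Hypothesis 3 has no stated model for moderators of product use, and lists undated use patterns as a moderator of exposure

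*Combined protocol and SAP*

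**What the plan says.** Section 2.0 states Aim 3 as "To determine important moderators of use of a product and exposure". Its own list of moderators is perception of the product and response to it after sampling, nicotine metabolite ratio, dependence, gender, race and age. Use is not on that list; it is one of the two things to be moderated. The opening of section 7.0 repeats the aim: "to determine important moderators for product use and exposure".

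The Hypotheses section places use between assignment, traits and exposure. Hypothesis 1 reads "Instructions for use will lead to significant differences in patterns of use, which will be related to biomarkers of exposure". Hypothesis 3 reads "Moderators for exposure will include pattern and intensity of tobacco product use", and then says that use will itself be affected by subjective responses and by "perception of safety of the product, gender, race, age, degree of dependence and nicotine metabolism phenotype".

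The Hypothesis 3 paragraph of section 7.0 describes a linear mixed model with time, group and "potential moderators (e.g., use patterns, age, sex, dependence, subjective responses, etc". It continues: "Interactions between group and the potential moderators will be included in the model and tested". The outcomes are given in brackets as total nicotine equivalents and total NNAL, with nothing to mark them as examples.

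**The concern.** Two things do not fit together.

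First, the aim has two outcomes, use and exposure, and the analysis has one. The second half of Hypothesis 3, that traits affect use, has no stated test.

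Second, use appears as a moderator without a date. By the plan's own account, on-trial use is changed by the randomised instruction and by the traits under study. A variable of that kind is an intermediate. Its interaction with group does not say for whom the instruction works differently, and holding it fixed removes whatever part of a trait's moderation acts through it.

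Section 3.0 says the moderator results should help set recruitment criteria for later trials. A trait that changes how people use the products under each instruction could go untested on use. Depending on the model, it could also be reported as unimportant for exposure.

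**Working it through.** **Step 1. Where use is an outcome in section 7.0.**

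| Place | Role of use | Tests group-by-trait on use? |
|---|---|---|
| General paragraph on outcomes | Tobacco use named as a primary outcome measure; mixed models for the primary aims | No moderator model stated |
| Hypothesis 2 | Cigarettes and snus topography as outcomes | No: time effects, separate model per group, no moderators |
| Hypothesis 3 | Use patterns as a moderator | No: outcomes are two biomarkers |
| Compliance paragraph | Compliance correlated with baseline covariates | No: compliance only |
| Other Analyses of Interest | Sampling-phase ratings and willingness to pay expected to predict later use | No model given; age, sex, race, dependence and metabolite ratio not covered |

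No row tests whether the Aim 3 traits change the effect of group on use. This finding needs no assumption.

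**Step 2. Which use is meant.** Pre-randomisation measures exist: snus use in the sampling week and diaries in the baseline smoking period (both section 6.4). The Hypotheses section, however, speaks of use that follows from the instructions, which is on-trial use. Section 7.0 does not settle it. Nor does it say whether moderators enter one model together or one at a time; the wording leans towards together.

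**Step 3. What a joint fit estimates.** Let G be group, M a baseline trait, U on-trial use and Y exposure.

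U = aG + bM + cGM + error
Y = kU + dGM + error

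Substituting, the GM coefficient in a model without U is kc + d. With U (and G×U) in the model it is d. With assumed c = 0.3 and k = 0.7:

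- d = 0: 0.7 × 0.3 = 0.21 without U, 0 with U.
- d = 0.21: 0.42 without U, 0.21 with U.
- d = −0.21: 0 without U, −0.21 with U.
- c = 0: d in both models, so no change.

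Simulation (2,000 runs, 276 per side) of the first two cases gave 0.21 and 0.00, with rejection rates of 53% and 6%, and 0.42 and 0.21, with power of 98% and 61%. With U as the outcome, the first case recovered c = 0.30 with about 93% power. When an unmeasured common cause of use and exposure was added to the first case, the joint model gave a group term of +0.20 and a GM term of −0.06, although both true direct effects are zero.

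**Step 4. How far power can move, and in which direction.** From the sample-size paragraph come 2 × 138 = 276 per side (complete against partial substitution) and 40 to 50% abstinence, taken as 45% at zero cigarettes in the complete-substitution arms. Everything else is assumed: M is dependence, NNAL rises 0.1 residual SD per cigarette, and the fit is at one time point, with no control arm and no dropout. Rejection rates for group-by-dependence on NNAL:

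| Assumed paths | Without use | With use and group-by-use |
|---|---|---|
| Dependence acts on use in complete arms only; all moderation (about 0.22 SD) through use | 66% | 6% |
| Same total, half through use | 67% | 23% |
| Same total, a quarter through use | 68% | 44% |
| Dependence acts on use with equal loading in both sides; no direct path | 6% | 5% |
| Equal loading plus direct moderation of 0.22 | 55% | 61% |
| Complete arms only, direct path opposing (−0.22) | 5% | 68% |

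The large losses all depend on dependence acting on use in the complete arms only. The documents do not say that. With equal loading the loss is negligible or becomes a small gain. In the last row the two models answer different questions: total moderation is about zero and direct moderation is not.

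**Step 5. The plan's own figure.** The 138 per group cannot be reproduced, because effect size, dropout rate and alpha are not given as numbers. The point does not depend on it.

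**The case against.** The best case for the plan has five parts.

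1. Use is not absent as an outcome. It is named as a primary outcome measure, and Hypothesis 2 models cigarettes and topography. This stands, and it rules out a reading someone might take, that the plan never models use. The gap is confined to moderators of use.

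2. Aim 3 already dates consumer response as after sampling, and Table 2 takes the metabolite ratio only at baseline. This also stands, so it would be wrong to infer that all the subjective moderators are undated. Dependence still needs a date: Table 1 has FTND and WISDM at screening and again on trial, and Aim 2 counts dependence among the on-trial responses ("subjective (e.g., dependence), biological (e.g., biomarkers of exposure) and behavioral responses").

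3. The list is illustrative, and harm to the exposure tests needs both on-trial use and a joint fit. True. Fitting moderators singly, or using sampling-phase or baseline use, leaves the baseline-trait tests intact. But the text permits the harmful version as readily as the harmless one, for a primary aim.

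4. Relating use to biomarkers is an intended question. Agreed. It is a question of association or mediation, and calling it moderation misdescribes it. Section 7.0 itself warns of selection bias when regression adjusts for compliance, which in the complete-substitution arms is largely a matter of cigarette use. Hypothesis 3 does not carry that caution over.

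5. A reader might take the fall from 66% to 6% as the likely cost. Step 4 does not support that.

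**Conclusion.** The point holds in two parts.

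Without conditions: one of the two outcomes of primary Aim 3 has no stated moderator model.

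With conditions: if use patterns means on-trial use, its interaction with group is not baseline effect modification; and if it is fitted jointly with the baseline traits, those tests estimate only moderation that does not act through use. The first condition is the more natural reading of the Hypotheses section and the second is favoured by the wording of section 7.0, but neither is fixed.

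The effect on power can be a large loss, nil or a gain, according to paths the documents do not give, so no power figure should be quoted as the expected harm. A reader might also infer that the group comparisons are compromised. They are not: the Hypothesis 1 intent-to-treat analysis does not adjust for use. The change should be made before analysis; it is not a threat to the trial's main comparison.

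**What to change.** Amend the Hypothesis 3 paragraph of section 7.0 as follows.

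1. Add on-trial use as an outcome, with the same baseline moderators and group interactions: cigarettes per day in all five arms, snus in the four snus arms.
2. Limit group-by-moderator tests to pre-randomisation measures. These are the Aim 3 list (product perception and response after sampling, baseline metabolite ratio, FTND and WISDM at screening, gender, race, age) plus sampling-phase snus use and baseline cigarettes per day. Leave on-trial use out of these models, and state whether the moderators are fitted together or singly.
3. Report on-trial use against biomarkers separately, as an association or mediation analysis labelled as open to unmeasured confounding.

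The cost is analysis wording and a few more models; every variable is already collected. On-trial use would no longer be reported as a moderator, and the separate use-biomarker analysis would remain exposed to unmeasured common causes.
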